Vitamin D and fatty acids Ω 3: role in the "honeymoon" of the Type 1 Diabetes of the child

The weight of diabetes on the child, on the family and in society

Type 1 diabetes (T1D) is an autoimmune disease in which there is a progressive reduction of insulin-secreting β -cells that involves the need to undertake replacement therapy with exogenous insulin.

The therapy consists of the administration of insulin in multiple administrations per day by pen or continuous infusion under the pump and requires frequent monitoring of capillary blood glucose or continuous glycemic monitoring with medical devices. T1D is burdened by important long-term complications: neurological, ocular, renal microangiopathic, which make diabetes the leading cause of chronic renal failure and dialysis, and acquired blindness. In addition, the pathology determines diabetic macroangiopathy, which leads to an increased risk of heart attack, macrovascular damage especially in the lower limbs with consequent diabetic foot and atherosclerotic complications of specific cardiac, cerebral and genital districts. These micro and macro-angiopathic complications, together with the continuous increase in the incidence and prevalence of diabetic pathology, cause a huge social and individual cost that currently represents a significant resource commitment, and will become an unsustainable health care expenditure in the years to come.

Data from the Pediatric Regional Register (0-15 years), reported in Literature, provide a precise assessment of the incidence of T1D in the Piedmont Region: from these data we can see an increase of 3.3% annually, with a consequent increase in direct costs of diabetes (in Italy for the NHS in 2012 direct costs over € 9 billion, 57% for hospital access, 30% for drugs and devices, 13% for outpatient care) and indirect and immaterial, which are even higher, even if hardly quantifiable. There was also a greater increase in incidence in pre-school and immigrant children, especially in relation to the dark color of the skin that limits the vitamin D biosynthesis.

The previous consideration, together with the prevalence of widespread vitamin D deficiency usually detected at the onset of T1D, led to a causal relationship between vitamin D deficiency and the genesis of diabetes. The essential role of this vitamin consists in the immunoregulatory activity on T-lymphocytes. Today, vitamin D supplementation in every child with diabetes, with 1000 IU / day (corresponding to the current indications of the Endocrine Society, IOS and SIPPS), and the monitoring of the actual serum concentration [as 25 (OH) D3] in the range 30-50 ng / ml, is a therapeutic act that is consolidating in the therapy of T1D.

In addition to a genetic condition of polygenic risk, which finds the greatest risk related to specific predisposing HLA alleles, there are no known causes of this autoimmune pathology, ie an event, presumably environmental, conditions the increased incidence of the disease especially in fast-moving countries socio-economic evolution. By logical deduction, genetic predisposition is stable, and the increase in incidence of T1D must be related to environmental factors (pollutants, infections, especially viral, or food changes), since the increase in T1D is observed in countries of all over the world, and in particular in developing countries. There are many possible environmental causes of the increase of T1D.

A vitamin D and omega 3 (Ω -3) deficiency status is reported in the general population, including the pediatric population. The lack of Ω -3 in our power supply could represent an environmental cause or an

amplifying factor a trigger event. In any case, the ratio between Ω -6 and Ω -3 has shifted from 1: 1 a few decades ago, to a current 10: 1 or 25: 1. In particular, a case-control study of Stene et al. in Norway (2000) showed that the intake of cod liver oil by the mother during pregnancy or during the first year of life was associated with a reduced risk of developing T1D. Stene concluded that vitamin D and long fatty acids omega-3 (Ω -3), eicosapentenoic acid (EPA) and docosahexaenoic acid (DHA) have a protective effect against the development of T1D. In a further study, Stene and Joner (2003) found that dietary supplementation of cod liver oil during the first year of life was significantly associated with a lower risk of developing T1D during childhood (OR 0.7, $p < 0.001$). This is consistent with a protective role played by vitamin D and Ω -3 during pregnancy and early childhood.

Usually the honeymoon phenomenon is exhausted within a year, even if a residual amount of secretion persists at least up to two years from the onset. The endogenous insulin secretion is quantifiable as C-peptide, which represents the conjugation peptide between chain A and B of pro-insulin, which after free cleavage in the portal circle molecules of C-peptide and insulin in molar ratio 1: 2. Unlike insulin that is rapidly degraded in the liver and tissues, the C-peptide passes the liver and is filtered by the unchanged renal glomeruli in the urine. C-peptide is not present in exogenous insulin of pharmacological origin. The endogenous insulin secretion is quantifiable as C-peptide. A persistence of C-peptide (also dosages 0.2 ng / ml) reduces the risk of complications, improves the metabolic compensation and reduces the number of hypoglycemic episodes, so at least one of its maintenance would be an important objective to preserve.

01/01/2017

The study is preliminary and aimed at identifying whether a therapy with Ω -3 could be of support in T1D especially in the first years of illness, when a persistence of a residual β -cell mass is presumable and it is possible to act better on the pro-inflammatory component (insulinitis).

Purpose of the study

The aim of the study is to evaluate whether a controlled administration of vitamin D and Ω -3, in the early years of the onset of T1D, can preserve the residual β -cell mass, evaluable with a reduced insulin need for a long time, with a persistent level of C-peptide, a lower glycemic variability compared to children who do not carry out this supplementation.

Secondary assessment is to perform a baseline assessment of the AA / EPA ratio in children with type 1 diabetes.

Subjects and Methods

The subjects will be recruited at the Diabetology Clinic of the Pediatric Clinic of the AOU "Maggiore della Carità" of Novara.

In particular, two groups of subjects will be included, subject to the signing of the informed consent:

1°,2°,3° the groups, with T1D onset in 2014, 2015, 2016, retrospectively were evaluated as historical controls before 2017.

4 group°: all children with T1D with disease onset in the years 2017, will receive omega 3 supplement (EPA + DHA 60 mg / kg / of), and will be compared from a metabolic point of view (in particular for the needs of insulin and glycated hemoglobin) according to the scheme outlined with the pre-supplementation data, deduced from the medical records retrospectively.

1°,2°,3° groups: after 2017 were allowed to enter in the study and were prospectively evaluated

supplementation omega-3

Group 1	Group 2	Group 3	Group 4 new onset	
	vs Group 1	vs Group 2	vs Group 3	
		vs Group 1	vs Group 2	

			vs Group 1	
2014	2015	2016	2017	2018

The analysis will allow to quantify the effects of omega-3 at different distance from the onset in terms of metabolic advantage (insulin units / Kg / die, glycated hemoglobin, etc.) and to evaluate if and how much supplementation after the onset may give metabolic advantages compared to other patients not yet supplemented.

To the T0, T3, T6 and T12 will be detected anthropometric parameters (weight, height, BMI, Tanner Stages, PAOS / PAOD), insulin therapy in progress (IU / Kg / die) with MDI (multiple daily injection) or CSII (continuous subcutaneous infusion) and metabolic parameters (C-peptide, coagulation, lipid profile, basal blood sugar, glycated hemoglobin, vitamin D). The C-peptide in particular allows us to evaluate the residual cell function, which provides a "direct" measurement of endogenous insulin secretion. The fasting C-peptide / glycemia ratio will also be evaluated, as an estimate of residual insulin secretion. Glycated hemoglobin is an expression of blood sugar in the last three months. A value of less than 7.5% is a sign of good compensation.

In addition, the glucometer data will be downloaded at each visit to evaluate the glycemc variability parameters (mean glycemia, DS). A DS of less than 50% of the mean blood glucose represents an index of stability. The use by all patients of the same meter, delivered at the time of inclusion in the study, will eliminate the bias given by the diversity of the medical device. Indication will be given to perform pre-meal glycemc controls three times a day, and occasionally after 2 hours from the meal, in order to calculate the glycemc variability.

An initial dosage of the blood levels of AA, EPA and DHA (and relative ratio) will be carried out by capillary sampling and application of a few drops of blood on absorbent paper for all subjects. Fatty acids are measurable in whole blood, with a lipidogram, in which each component of FFA is selectively differentiated, and then quantified the individual fractions. In particular we will evaluate the ratio between 20: 4 Ω -6 arachidonic acid (AA), precursor of pro-inflammatory cytokines, and EPA, precursor of anti-inflammatory cytokines; this ratio represents a balance between the effector pre-metabolites of inflammation, which determine the apoptotic degeneration of β -cells, and the anti-inflammatory ones, which preserve a cellular share with an insulin secretive function. This value AA / EPA <3 is proposed in Literature for adults or patients with other diseases, but has also been used for children.

The measurement will be carried out free of charge at the Department of Pharmacological and Biomolecular Sciences (DiSFEB), Faculty of Pharmaceutical Sciences, University of Milan.

An assessment of the dietary intake of EPA and DHA fatty acids will be carried out for all the subjects included in the study through an interview with the dietician and the compilation of a frequency food questionnaire. The collection of the food questionnaire will take place at the time of enrollment (T0) and 12 months after supplementation with omega 3. All healthy control subjects will be submitted to the food questionnaire. Nutritional indications will be given to all families in order to optimize an optimal dietary introduction of fatty acids as indicated by the LARNs.

Supplementation

The intervention under study is only the administration of omega-3, to all patients with onset in recent years (2014-2018) with a contribution of 60 mg / kg / day of the sum of EPA and DHA (corresponding respectively to acid eicosapentenoico and docaesoenoico). The AA / EPA ratio will be monitored (arachidonic acid, Ω -6 / eicosapentenoic acid Ω -3), to reach the optimal range <3 , as indicated in the literature.

The chosen preparation will be omega-3, of extraction from fish, with a high concentration and purified to exclude mercury and lead, commercially available in stores and supermarkets. EnerZona. Equipe Enervit Srl will provide free Ener Zone, in capsules, from EPA 400 mg + DHA 200 mg, or capsules from EPA 200 mg + DHA 100 mg, or liquid solution, for subjects unable to swallow capsules or intolerant gluten capsules themselves; this will allow us to provide precise delivery and the same preparation to each patient.

All of our patients are supplemented with vitamin D. As vitamin D also has an immunomodulatory role it will be monitored in the study, and being frequently low at onset will be given at 1000 IU / day, as indicated in prophylaxis for children and adolescent; its level [as 25 (OH) D] will be controlled to reach the optimal values (established by Endocrine and other scientific societies) of 40-50 ng / ml, and possibly increased or reduced.

Inclusion criteria:

All children with autoimmune T1D, debuted in the years selected at the Pediatric Clinic of Novara. Some children with T1D in the wake of the published anecdotal case, have already spontaneously begun to supplement with omega 3, and will be excluded from the study. We have primarily considered our series of children with T1D onset according to the ADA, ISPAD and SIEDP criteria of the years 2015, 2016 and 2017, since insulin secretive activity persists for at least two years from the onset.

Exclusion criteria:

pathologies such as:

- coagulation defects
- renal diseases (nephrotic syndrome, calculosis, renal cysts, etc.)
- sarcoidosis, histoplasmosis

01/01/2017

- endocrinological diseases (hyperparathyroidism)
- tumoral pathologies or tuberculosis

Gluten intolerance (CD) or thyroiditis in T1D are not exclusion criteria.

Chronology of investigations and time of execution of the study

T.0 Signature of informed consent. Baseline auxological and metabolic evaluation (IU / Kg / day exogenous insulin) by means of examination, assessment of dietary intake through food questionnaire and interviews with dietician, blood tests (vitamin D, AA / EPA, C-peptide, basal glycemia, glycated hemoglobin, lipid profile, coagulation). Discharge of glucometer data for glycemic variability. Start supplementation with vitamin D, in case of deficiency, if subject not already supplemented. Begin supplementation with EPA + DHA, in case of deficiency, if willingness to recruit.

T.3 at 3 months from the beginning of the supplementation, only for the subjects supplemented with omega 3. Auxological and metabolic evaluation (IU / Kg / day exogenous insulin) by examination, blood tests (AA / EPA, C-peptide, basal glycemia, glycated hemoglobin, lipid profile, coagulation). Discharge of glucometer data for glycemic variability.

T.6 to 6 months from start of supplementation, only for subjects supplemented with omega 3. Auxologic and metabolic evaluation (IU / kg / exogenous insulin) by examination, blood tests (AA / EPA, C-peptide, basal blood sugar, glycated hemoglobin, lipid profile, coagulation). Discharge of glucometer data for glycemic variability.

T.12 At 12 months from the beginning of the study, will be re-evaluated for all subjects, all the previous auxological, metabolic and biochemical parameters and a new evaluation of the dietetic dike of fatty acids will be carried out.

Study security and caution of the subject included

The safety of the therapy with supplements is reflected in the extensive experience of using cod liver oil which in the past has been a routine supplement for children for several years.

High doses of Ω -3 over 5 g / day could result in a longer bleeding time, which is why coagulation monitoring is required, even if supplementation is required at doses of less than 5 g / day. With the use of Ω -3 a reduction of triglyceride levels is observed, which could represent a clinical advantage for the subject and a precise therapeutic objective often sought by the practitioners. A triglyceride evaluation will be performed pre-supplementation and at 12 months from the beginning of the same.

Financial resources and expected costs

01/01/2017

Enervit supplies Ener Zone Omega 3 RX in capsules containing each EPA 400 mg + DHA 200 mg and in liquid formulation for younger children and / or with concomitant celiac disease. Ascensia Diabetes Care supplies Conturnext USB and Conturnext strips, to allow frequent blood glucose measurements, with accuracy and precision.

The blood chemistry tests are part of the normal T1D treatment routine. The dosage of the different metabolic and hormonal parameters at the time T1 will be borne by the Pediatric Clinic. The AA / EPA report will be determined by the Department of Pharmacological and Biomolecular Sciences DiSFEB, Faculty of Pharmaceutical Sciences of the University of Milan free of charge. Other possible findings as coagulation will be calculated as expenditure "study use" of the Pediatric Clinic.

DATA PROTECTION

to. Blood samples collected on Guthrie cardboard sent to Milan will be collected with the informed consent of the parents.

b. For the protection of the subject and clinical data, withdrawals will be identified with a code.

c. The clinical data will be managed by clinical referents inside Pediatrics ([name], [name]) and the name of the subject will be identified by initial name and surname

d. The withdrawals will be stored in the Laboratory of Milan Pharmacy University of the Maggiore Hospital under the exclusive control of the laboratory referents ([name])

Statistic analysis

The data will be expressed as a mean \pm SD. For continuous variables, the variations between the groups are compared by means of the averages calculated with the non parametric Wilcoxon and Mann-Whitney U tests. The variability of the biochemical parameters over time will be evaluated by means of tests for repeated measurements. A correlation analysis will be performed with the Pearson correlation test, after adequate logarithmic transformation of the parameters when necessary. Multiple regression analysis will be used to evaluate associations between variables. Statistical significance will be assumed for values of $p < 0.05$. All statistical analyzes will be performed with the SPSS program for Windows version 22.0 (SPSS INC; Chicago, IL, USA).

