## Statistic analysis

The data will be expressed as a mean  $\pm$  SD. For continuous variables, the variations between the groups are compared by means of the averages calculated with the non parametric Wilcoxon and Mann-Whitney U tests. The variability of the biochemical parameters over time will be evaluated by means of tests for repeated measurements. A correlation analysis will be performed with the Pearson correlation test, after adequate logarithmic transformation of the parameters when necessary. Multiple regression analysis will be used to evaluate associations between variables. Statistical significance will be assumed for values of  $p < 0.05$ . All statistical analyzes will be performed with the SPSS program for Windows version 22.0 (SPSS INC; Chicago, IL, USA).

All children with T1D with disease onset in the years 2017, will receive omega 3 supplement (EPA + DHA 60 mg / kg / of), and will be compared from a metabolic point of view (in particular for the needs of insulin and glycated hemoglobin) according to the scheme outlined with the pre-supplementation data, deduced from the medical records retrospectively.

supplementation omega-3 ↓

Group 1 n.	Group 2 n.	Group 3 n.	Group 4 new onset	
	vs Group 1	vs Group 2	vs Group 3	
		vs Group 1	vs Group 2	
			vs Group 1	
2014	2015	2016	2017	2018

The analysis will allow to quantify the effects of omega-3 at different distance from the onset in terms of metabolic advantage (insulin units / Kg / die, glycated hemoglobin, etc.) and to evaluate if and how much supplementation after the onset may give metabolic advantages compared to other patients not yet supplemented.

Further statistical analysis could be performed if appropriate.

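### Group 4's supplemented values date from 2017 onward and its control values from before 2017, yet the plan specifies no drift check or calendar term to separate year-to-year change from omega-3

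*Protocol*

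**What the plan says.** The Protocol (Subjects and Methods) defines Groups 1 to 3 by onset in 2014, 2015 and 2016 and says they "retrospectively were evaluated as historical controls before 2017". For Group 4, "all children with T1D with disease onset in the years 2017, will receive omega 3 supplement". The SAP (Statistic analysis) has Group 4 compared "according to the scheme outlined with the pre-supplementation data, deduced from the medical records retrospectively".

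The scheme, printed in both documents, lists six pairs: Group 4 against 3, 2 and 1, and also 2 v 1, 3 v 2 and 3 v 1. No pair has a calendar window or a time since onset attached. One purpose is given for the whole scheme: "The analysis will allow to quantify the effects of omega-3 at different distance from the onset in terms of metabolic advantage".

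Groups 1 to 3 also "after 2017 were allowed to enter in the study and were prospectively evaluated". The Protocol's Supplementation section gives omega-3 to all patients with onset from 2014 to 2018. The Chronology section instead makes the start conditional on deficiency and willingness, limits T3 and T6 to supplemented subjects, and holds T12 for everyone.

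The methods are unadjusted rank tests between groups, unspecified repeated-measures tests and a general multiple regression. Neither document names calendar year, cohort or drift as a term. The group sizes in the SAP scheme are blank.

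**The concern.** In the Group 4 comparison a control value is one recorded before 2017 and a supplemented value is one recorded from 2017. Anything that changed between those periods (insulin dosing habits, technology, assays, completeness of the charts) enters the contrast together with omega-3. Adjusting for the children's characteristics does not remove a period effect.

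The exposure grows with the gap: one year for Group 4 v 3, two for v 2, three for v 1. Some changes arrive with study entry itself. The Protocol issues a common glucose meter at inclusion and gives dietary advice on fatty acids to all families, and the retrospective chart values predate both.

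The data needed to gauge ordinary year-to-year change are partly in hand, because three consecutive cohorts have unsupplemented chart values. The plan lists the pairs that could show it but does not define them for that use.

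**Working it through.** The documents contain no sample size, power, effect size or SD, so there is no planned figure to reproduce. Two checks were made.

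**1. What can be separated from what.** Take the 14 cells formed by onset year (2014 to 2017) and calendar year (onset year to 2018), code supplementation as calendar year 2017 or later, and include time since onset as a factor.

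| Calendar effect in the model | Columns | Rank | Omega-3 term estimable? |
|---|---|---|---|
| none | 6 | 6 | yes |
| linear | 7 | 7 | yes |
| free year effects | 10 | 9 | no |

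Smooth drift can therefore be estimated and removed. A step in 2017 cannot. The pre-2017 information lies in six cells: Group 1 in years 0, 1 and 2 from onset, Group 2 in years 0 and 1, Group 3 in year 0.

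**2. Error rate if drift is ignored.** Assumptions: no omega-3 effect, n children per cohort, linear drift of b SD per year, two-sided 5% test (sidedness is not stated), and a normal approximation in place of the rank test.

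For a pair k years apart, the shift in standard errors is d = bk / √(2/n), and the rejection rate is Φ(d − 1.96) + Φ(−d − 1.96). Example with n = 20, b = 0.1, k = 3: d = 0.3 / 0.316 = 0.95, giving 15.8%.

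| b (SD/year) | n | 4 v 3 | 4 v 2 | 4 v 1 |
|---|---|---|---|---|
| 0.1 | 10 | 5.6% | 7.3% | 10.3% |
| 0.1 | 20 | 6.2% | 9.7% | 15.8% |
| 0.1 | 30 | 6.7% | 12.1% | 21.3% |
| 0.2 | 10 | 7.3% | 14.5% | 26.9% |
| 0.2 | 20 | 9.7% | 24.4% | 47.5% |
| 0.2 | 30 | 12.1% | 34.1% | 64.2% |

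If years vary at random with SD τ instead of drifting, the variance of a pairwise difference is inflated by 1 + nτ². With n = 20, the error rate is 14.4% at τ = 0.2 and 24.1% at τ = 0.3.

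**3. Price of a trend adjustment.** Against the pooled Groups 1 to 3, the variance of the Group 4 contrast is (1 + 1/3)/n = 1.33/n. Projecting a line through onset years 2014, 2015 and 2016 to 2017 (distance from their mean 2, sum of squares 2) gives (1 + 1/3 + 2²/2)/n = 3.33/n. The ratio of standard errors is √2.5 = 1.58. The difference detectable with 80% power rises from 1.02 to 1.62 SD (n = 10), 0.72 to 1.14 SD (n = 20), or 0.59 to 0.93 SD (n = 30).

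This is a best case, because it needs all three cohorts. A child with onset in 2016 reaches 12 months in 2017, so at 12 months only Groups 1 and 2 have pre-2017 values. A line through two cohorts gives (1 + 1/2 + 2.5²/0.5)/n = 14/n against a pooled 1.5/n, a ratio of √9.33 = 3.1.

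**The case against.** A reader might infer that the plan never uses its unsupplemented cohorts. The documents do not support that. The scheme lists 2 v 1, 3 v 2 and 3 v 1. Read with pre-2017 values, these compare unsupplemented children with unsupplemented children; read with later values for the newer cohort, they are omega-3 contrasts. The plan does not say which, and assigns no purpose pair by pair. What stands is that they are listed without a window and not designated as a drift check.

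A reader might also infer that omega-3 and calendar time cannot be separated at all. That is too strong. Linear drift is estimable. T0 values of Groups 1 to 3 are taken in the study period before omega-3 starts. The Chronology section also hints at children followed without supplementation, although the Supplementation section says all receive it. Full inseparability holds only for a step in 2017 or free year effects.

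Evidence of actual drift is thin. The Protocol's background says vitamin D supplementation "is a therapeutic act that is consolidating in the therapy of T1D", but that describes care in general; for this clinic the Supplementation section says all its patients already receive it. No passage reports a change in dosing, assays or recording. The drift sizes are therefore illustrations. This limits the size of the claim, but not the point that the plan has no means of checking.

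A tempting remedy is to credit omega-3 only with differences larger than the largest one among Groups 1 to 3. It performs poorly. Those groups span two years of drift and Group 4 v 1 spans three. In a simulation with 20 per cohort, false attribution for Group 4 v 1 fell only from 48% to 40% at 0.2 SD per year. With no drift at all, the largest difference still averages 0.38 SD through sampling noise.

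**Conclusion.** The concern holds in this form: the Group 4 comparison confounds calendar drift with omega-3, and neither document specifies a drift check, a calendar term or the data windows that would let the listed pairs serve as one. As planned, steady drift of 0.1 SD per year would give a false-positive rate of 10 to 21% for Group 4 v 1, and 0.2 SD per year 27 to 64%, with 10 to 30 children per cohort. Group 4 v 3 is much less exposed, at 6 to 7% and 7 to 12%. Drift sizes and cohort sizes are assumptions, and nothing in the documents shows that drift of this size occurred. The study calls itself preliminary, so this is an improvement the plan should make rather than a reason to discard the design. A trend adjustment brings the error back to about 5% if drift is linear, but does not protect against a change that coincides with study entry.

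**What to change.** In the SAP:

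- **(a)** State the calendar window and months since onset for every listed pair.
- **(b)** Designate 2 v 1, 3 v 2 and 3 v 1, restricted to pre-2017 unsupplemented values at equal months since diagnosis, as the drift check. Report estimates with confidence intervals and attach no largest-difference decision rule. Say that Group 3 can contribute only its early months.
- **(c)** Report each Group 4 contrast with and without a linear onset-date trend estimated from the unsupplemented data, as a sensitivity analysis.
- **(d)** Use T0 values only as a supplementary near-contemporaneous comparison, mainly for Group 3 children whose months since diagnosis match. If onset is uniform over 2016 and T0 falls in January to March 2017 or is spread over 2017, 37 to 44% of Group 3 have T0 at 9 to 15 months from onset: about 7 to 9 of an assumed 20. Groups 1 and 2 are largely beyond their first year.
- **(e)** Reconcile the Protocol's Supplementation section (all patients supplemented) with its Chronology section (conditional start, T3 and T6 only for supplemented subjects), so that it is clear whether unsupplemented children exist after 2017.

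The cost is SAP wording and extra analysis of chart and T0 data already collected or planned; no new patients or visits are needed. The adjusted contrast has a standard error about 1.6 times that against pooled controls, more where Group 3 has no pre-2017 value, and it relies on linear drift. A step in 2017, including the common meter and the dietary advice, stays inseparable from omega-3, and the conclusions should say so.

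### Comparing supplemented children with pre-2017 records estimates the effect of the whole study programme, not of omega-3 alone, because advice, meter, strips and study visits start with the capsules

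*Protocol*

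**What the plan says.** The protocol (Supplementation) declares: "The intervention under study is only the administration of omega-3". The SAP (Statistic analysis) says: "The analysis will allow to quantify the effects of omega-3 at different distance from the onset", and the protocol's Subjects and Methods makes the same statement.

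The protocol also introduces the following at study entry:

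- **Dietary advice** (Subjects and Methods, paragraph on dietary intake): "Nutritional indications will be given to all families in order to optimize an optimal dietary introduction of fatty acids as indicated by the LARNs". It comes with a dietician interview and a food questionnaire.
- **Meter and testing** (Subjects and Methods): "The use by all patients of the same meter, delivered at the time of inclusion in the study", together with "Indication will be given to perform pre-meal glycemc controls three times a day". Under Financial resources and expected costs, a company "supplies Conturnext USB and Conturnext strips, to allow frequent blood glucose measurements, with accuracy and precision".
- **Visits** (Chronology of investigations): the T3 and T6 evaluations are restricted to supplemented children. T12 covers everyone.

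The comparators are the 2014, 2015 and 2016 onset cohorts, used as historical controls for the period before 2017, with data taken from medical records (protocol, Subjects and Methods; SAP). Groups are compared with Wilcoxon and Mann-Whitney tests. Multiple regression is mentioned for associations in general, with no covariates named.

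**The concern.** Several things change between the control observations and the supplemented observations, and the study itself introduces them. This is separate from differences in patient mix between onset years, so matching or adjusting on patient characteristics would not remove it.

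The elements bear on what is measured. Insulin need and HbA1c, which the group comparison singles out, can respond to testing, diet and follow-up. The SD of meter readings depends on when readings are taken, so a prescribed schedule may make it non-comparable with earlier records. The dietary advice targets fatty-acid intake, the same exposure as the capsules, so a fall in AA/EPA after T0 also has two possible sources.

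If omega-3 did nothing and the rest of the programme helped, supplemented children could still look better than the records. Under the present wording, that difference would be reported as an omega-3 effect.

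**Working it through.** The documents give no sample size, SD, target effect or power, and the group sizes in the SAP scheme are blank. There is no planned figure to reproduce, so the check is mainly a comparison of sections.

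**1. What differs between the two sides of the contrast**

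| Element | Supplemented children | Pre-2017 records |
|---|---|---|
| Omega-3 | Yes | No |
| Study advice on dietary fatty acids | Yes | Not as a study procedure; usual counselling not described |
| Common meter, supplied strips, testing instruction | Yes | Not as a study procedure; usual testing not described |
| T3 and T6 study evaluations | Yes | Not as a study procedure; usual visit frequency not described |
| Calendar period | 2017 onward | Before 2017 |

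Giving advice to all families and the same meter to all patients balances children observed within the study. It does not balance observations made before the study began.

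**2. What the contrast estimates**

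Assume for simplicity that effects add. Let θ be the effect of omega-3, b the effect of the other study procedures relative to the controls' usual care, and c any period effect. The expected difference is

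D = θ + b + c.

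The data identify D only. The study procedures coincide with group membership, so an indicator for them added to a regression would be collinear with group. If θ = 0, then D = b + c, whatever the sample size.

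**3. Illustration of the consequence**

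Assumptions, none of them from the documents: θ = 0, c = 0, equal groups of n, outcome SD of 1, and a normal approximation to a two-sided test at 0.05. The documents give the 0.05 level but not the sidedness. With SE = √(2/n),

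P(p<0.05) = Φ(b/SE − 1.96) + Φ(−b/SE − 1.96).

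For n = 20 and b = 0.5: SE = √0.1 = 0.316 and b/SE = 1.581, so P = Φ(−0.379) + Φ(−3.541) = 0.353.

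| n per group | b = 0 | b = 0.2 | b = 0.3 | b = 0.5 |
|---|---|---|---|---|
| 15 | 5.0% | 8.5% | 13.0% | 27.8% |
| 20 | 5.0% | 9.7% | 15.8% | 35.3% |
| 30 | 5.0% | 12.1% | 21.3% | 49.1% |
| 40 | 5.0% | 14.5% | 26.9% | 60.9% |

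The error rate stays at 5% if the procedures change nothing, and rises with both b and n otherwise. The table shows direction and sensitivity; it does not estimate b.

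**The case against.** **Usual care may have been similar.** The protocol's introduction describes frequent glucose monitoring as part of T1D therapy, and the section on costs calls the blood tests routine. A reader might infer that the controls had no dietary advice, little testing and fewer visits. The documents do not say so. They establish only that the study-specific versions were absent. Nor do they say that T3 and T6 exceed normal clinic follow-up, or that the strips were free; they say the strips were supplied. This objection stands as a limit on size: b could be close to zero. It does not restore the claim, since nothing in the plan shows that b is zero.

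**The meter and schedule are measurement standards.** The protocol gives their purpose as removing device differences and calculating glycemic variability. That is fair within the study, but they cannot standardise readings taken earlier. No case is made here that testing or visits would change C-peptide, which the protocol regards as the direct measure of secretion. The aim names insulin need, C-peptide and glycemic variability; HbA1c enters through the group comparison.

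**Not every contrast need be affected.** A reader might conclude that every cell of the comparison scheme uses pre-study charts. The table is damaged in the text available, so that cannot be confirmed. Groups 1 to 3 could later enter and be followed prospectively, the protocol mentions patients not yet supplemented, and the T0 entry makes supplementation conditional. If concurrent unsupplemented children exist, advice and meter would be balanced against them, though T3 and T6 would not. No such comparison is specified, so the point is confined to contrasts with pre-2017 records.

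**The word 'only' may simply mark omega-3 as the test agent, with vitamin D as background.** That is a reasonable reading. The SAP's promise to quantify omega-3 effects still depends on the same contrasts.

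**Conclusion.** The point holds for contrasts of supplemented children with pre-2017 records. These estimate the effect of the study programme against earlier care, plus any period effect. They cannot isolate omega-3, and the unadjusted tests do nothing to separate the components.

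The size cannot be derived from the documents. A reader might want to express the bias in HbA1c points, but there is no figure to support one. It may be small if usual care already resembled the programme. The conclusion rests on two readings of the text: that the advice, meter, testing instruction and T3/T6 evaluations begin at study entry, and that the control data come from records made before 2017. Describing the study as preliminary makes a cautious claim easier to accept, but does not change what is estimated.

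**What to change.** 1. **Restate the claim** in the protocol (Subjects and Methods; Supplementation) and in the SAP (Statistic analysis). Describe the estimated effect as that of the study programme (omega-3, dietary fatty-acid advice, supplied meter and strips with a testing instruction, and study visits) compared with pre-2017 care. Do not attribute a difference to omega-3 alone.
2. **Describe the controls' care.** Where charts allow, abstract diet counselling, testing frequency and visit frequency for the historical controls, and report them beside those of the supplemented children. This shows readers how large the difference in care could be.
3. **Keep within-group regression exploratory.** A regression of outcome change on change in AA/EPA among supplemented children may be reported as support, with adherence confounding acknowledged: children who take capsules reliably may also manage insulin better. AA/EPA is a post-baseline variable, and because the protocol aims for a ratio below 3 throughout, it may vary too little to reveal a real effect. It should not serve as a rule for crediting benefit to omega-3.

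Cost: wording changes in both documents, a little more chart abstraction, and a narrower headline claim.
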